#### STATISTICAL ANALYSIS PLAN

The goal of this analysis was to observe the effect of the probiotic on plasma concentrations of sCD14, sCD163, LBP, IL-6, IL-8, IL-10, MCP-1, and TNF-α. Of the 16 eligible participants who initiated the probiotic, 14 participants completed the probiotic course, and two were lost to follow-up prior to completion. Ten participants returned after the washout period for Visit 4. Descriptive statistics were obtained on demographic characteristics and drinking history. All collected datapoints were considered for analysis regardless of probiotic completion or loss to follow-up. Biomarker concentrations greater than three standard deviations from the mean were excluded to limit the impact of statistical outliers on the analysis. Regarding undetectable biomarker values, sCD14 had 3.7% missing data (n=2), IL-6 had 35% missing data (n=19), IL-10 had 5.6% missing data (n=3), LBP had 1.8% missing data (n=1), and MCP-1 had 5.6% missing data (n=3). There were no undetectable biomarker values for IL-8, sCD163, or TNF-α. Regarding outlier exclusions, IL-6 had one outlier value, IL-8 had two outlier values, LBP had one outlier value, sCD163 had one outlier value, and TNF-α had one outlier value. Distributions for sCD14, IL-10, and MCP had no outlier values.

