Linear mixed models were used to assess changes in biomarkers over the study period. Models included the effect of alcohol use variables (assessed at Visit 1, Visit 3, and Visit 4) as time-varying covariates, specifically, number of heavy drinking days, total number of drinking days in, total number of standard drinks, and days since last drink. Self-reported alcohol use variables were treated as continuous. Self-reported drinking variables were assessed for collinearity and included in the final model if they met an acceptable variance inflation factor (VIF) <10. Total number of standard drinks was dropped from the final model due to high VIF. Despite prior evidence for sex effects on alcohol consumption and its impacts, there were too few females to test for this effect, and sex was not included in models. Models were specified to identify participant as the subject variable and visit number (1, 3, and 4) as the repeated measure, and with fixed slope and intercept. An autoregressive variance-covariance structure was selected for optimal model fit based on the Akaike Information Criterion (AIC). In the primary model (Model 1), the trajectory of biomarker concentrations before, during, and after probiotic use were examined, with alcohol variables (number of heavy drinking days, number of drinking days, and days since last drinks) included as time-varying covariates. In Model 1, biomarker

concentrations below the threshold of detectability were treated as missing data in analyses. Of note, maximum likelihood estimation as applied in the linear mixed model approach is able to handle missing data without excluding cases listwise or imputing data, thus making full use of the available data and minimizing bias in parameter estimates (Baraldi & Enders, 2010). To assess for non-linear changes in biomarker concentrations, a secondary model (Model 2) was tested to include a quadratic effect of time for the biomarker outcomes. Finally, a sensitivity analysis model (Model 3) was tested to assess for the effect of data missing at random. In Model 3, data below the detectability threshold of the assay (i.e., missing) were imputed at half the value of the threshold per the manufacturer. All analyses in this paper were conducted using SAS software, version 9.4 for Windows (SAS Institute, Cary NC.)

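### Model 2's quadratic-time test can be anti-conservative, mainly because maximum likelihood is named with no small-sample correction for at most 40 rows, and to a lesser degree because autoregressive lags are indexed by visit number

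*Combined protocol and SAP*

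**What the plan says.** The Statistical Analysis Plan specifies the repeated index and Model 1 as "visit number (1, 3, and 4) as the repeated measure, and with fixed slope and intercept". On covariance it says: "An autoregressive variance-covariance structure was selected for optimal model fit based on the Akaike Information Criterion (AIC". It does not list the structures that were compared, the form of autoregression, or a lag in days.

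The only estimator it mentions is "maximum likelihood estimation as applied in the linear mixed model approach", in a remark about missing data. It states no degrees-of-freedom method, REML option or small-sample correction.

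Model 2 has a stated purpose, "To assess for non-linear changes in biomarker concentrations", and is described thus: "a secondary model (Model 2) was tested to include a quadratic effect of time for the biomarker outcomes". Whether time means visit number or days is not said. The outcomes are "plasma concentrations of sCD14, sCD163, LBP, IL-6, IL-8, IL-10, MCP-1, and TNF-α".

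On numbers: "Of the 16 eligible participants who initiated the probiotic, 14 participants completed the probiotic course", and "Ten participants returned after the washout period for Visit 4". Part III, section 3 (Materials, Methods and Analysis) puts Visit 3 at 30 days after starting the supplement, give or take 5, and Visit 4 at one to ten months after the course ends.

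**The concern.** Visit 4 is the washout visit. A marker that moves on the probiotic and returns afterwards shows up as curvature, so Model 2 is where that pattern would be detected. If the standard error of the quadratic term is too small, noise can be read as an on-treatment change that reversed.

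Two features could shrink it. First, ML divides the residual sum of squares by the number of rows and ignores the fixed effects already estimated, which matters with about 40 rows. Second, the natural reading of an autoregressive structure over visit number gives Visits 1–3 and Visits 3–4 the same correlation, although the second gap can be many times longer and differs between participants.

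**Working it through.** The plan gives no alpha, power or degrees of freedom for these models, so there is no design figure to reproduce.

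**Rows.** Visits 1, 3 and 4 give at most 16 + 14 + 10 = 40. As a cross-check, the reported undetectable percentages fit a denominator of 54 (2/54 = 3.7%, 19/54 = 35%, 3/54 = 5.6%). That equals 16 + 14 + 14 + 10 if Visit 2, which is not modelled, had 14 participants. Forty is an upper bound: undetectable values and outliers reduce it, probably most for IL-6 (19 undetectable over all visits).

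**Parameters.** Intercept, time and three alcohol covariates make 5 fixed effects in Model 1. The quadratic term makes 6 in Model 2. Residual df in Model 2 are 40 − 6 = 34; within-person df are 40 − 16 − 5 = 19.

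**ML shrinkage alone.** The standard error shrinks by 1 − √((n − p)/n). Model 1: 1 − √(35/40) = 6.5%. Model 2: 1 − √(34/40) = 7.8%.

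**Why lags matter here.** With time coded 1/3/4, Model 2 is saturated over visits, and the quadratic coefficient is m₁/6 − m₃/2 + m₄/3, where m is the adjusted visit mean. Its variance depends directly on the Visit 1–3 and 3–4 correlations that the structure sets equal.

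**Simulation under no change over time.** Inputs from the documents: 16/14/10 participants, Visit 3 at day 25–35, three time-varying covariates. Assumptions: two-sided 5%, normal outcomes, Visit 4 gap uniform on 30–300 days, homogeneous AR(1), time coded 1/3/4, and the true correlations below. There were 8,000 runs per case (Monte Carlo error about 0.3 points). The t reference has 19 df. Type I error of the quadratic term, fitting AR by visit:

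| Assumed true correlation | ML, t | REML, t | REML, Kenward-Roger | ML standard error too small by |
|---|---|---|---|---|
| AR by visit, 0.6 | 7.4% | 5.2% | 4.5% | 11% |
| Decay by day, 0.7 at 30 days | 10.4% | 7.7% | 7.0% | 20% |
| Constant, 0.6 | 9.9% | 7.2% | 6.1% | 17% |
| Half stable, half decay | 12.9% | 9.4% | 8.0% | 24% |

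A second simulation of the same cases gave 7.8, 11.8, 9.2, 13.6% (ML) and 5.2, 8.6, 6.5, 10.0% (REML, t). The Kenward-Roger column rests on one simulation. A wider set of 24 combinations of correlation and time coding gave 6.2–15.1% (ML, t) and 4.1–11.3% (REML, t).

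**Split of the excess.** Excess over 5% with ML: 2.4, 5.4, 4.9, 7.9 points. With REML and Kenward-Roger: −0.5, 2.0, 1.1, 3.0. Share removed in the last three rows: 3.4/5.4 = 63%, 3.8/4.9 = 78%, 4.9/7.9 = 62%; in the first row, all of it. What remains is lag misfit. The split depends on which problem is corrected first: on the standard-error scale the two are closer (11% too small with correct lags, 17–24% with wrong ones).

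**Expected false quadratic results over eight markers** (8 × rate; independence not needed). Correct test: 8 × 0.05 = 0.40. ML: 8 × 0.074 = 0.59 to 8 × 0.136 = 1.09. Kenward-Roger: 8 × 0.045 = 0.36 to 8 × 0.080 = 0.64.

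**Time in days instead.** AR by visit with REML and t gives 4.1–4.9% under constant correlation, but 6.3–7.5% under decay and 7.6–8.8% under the mixture.

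**Model 1 slope, time coded by visit.** ML: 6.4, 4.7, 3.9, 3.8%. REML with Kenward-Roger: 4.2, 3.2, 2.4, 2.2%.

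**The case against.** **The estimator is not firmly stated.** ML appears only in a remark on missing data, and the software settings may have supplied REML or a t reference. This stands: the ML figures are conditional, and the REML figures belong beside them.

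**AIC chose the structure.** This protects little. In the three cases where AR by visit is wrong, it still beat compound symmetry and independence in 64, 30 and 68% of REML runs. In those runs the quadratic error was 7.9, 7.7 and 8.6% even with Kenward-Roger. The plan does report one structure for eight markers, which makes the constant-correlation case less likely: if markers were independent, a 30% win rate would give at least 5 of 8 only about 6% of the time. The decay cases are not weakened in this way.

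**The gaps are assumed.** With Visit 4 gaps of 30–60 days, REML with t gives 6.1% under decay and 6.6% under the mixture; constant correlation does not improve (7.8%). The size therefore depends on a spread that the documents give only as a range.

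**It is a secondary model in a pilot.** True. No decision rule hangs on it, and section 4 (Participant Population) describes the aim as preliminary data. This limits the severity.

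A reader might infer that unequal visit spacing is the main fault, or that the primary Model 1 results are unsafe. The documents and figures support neither. Most of the excess disappears with small-sample correction while the equal lags are kept, and the visit-coded Model 1 slope stays at about 4–6% with ML.

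**Conclusion.** The point holds as a possibility, not as a demonstrated error. If ML was used without correction and time was coded by visit, the quadratic test in Model 2 runs at about 7–14% instead of 5%. REML with a t reference brings this to about 5–10%, and Kenward-Roger to 4.5–8.0%.

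The main cause, judged by what correction removes, is ML on at most 40 rows; equal lags account for the smaller remainder. These sizes rest on assumed correlations, gaps and covariates, and on an estimator, time scale and autoregressive form that the plan leaves unstated. Some scenarios show no inflation. It would go too far to conclude that any reported quadratic effect is false.

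Severity is minor to moderate and is confined to a secondary model in a pilot.

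**What to change.** Refit Models 1–3 with METHOD=REML and DDFM=KR. State the estimator, the df method, the time scale, the autoregressive form and the structures compared by AIC. Keep the chosen structure as the main fit.

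Beside Model 2, report one fit without equal lags. The plan is written in the past tense, so label this fit a post hoc sensitivity analysis:

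- If visit dates exist, use spatial power on actual study day. With REML and t it gave 2.4–5.7% over the 24 combinations. The documents do not say whether dates were kept.
- Otherwise use compound symmetry, and only if time is coded by visit. With time in days it can be worse than AR by visit: 8.8% and 11.1% under decay and mixture, against 7.5% and 8.8% (REML).

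An unstructured matrix shows no clear gain (6.0–6.7% with Kenward-Roger). Call a quadratic effect robust only if it also holds in the sensitivity fit.

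The cost is two SAS options and one extra fit per marker, with slightly wider intervals. The Model 1 slope test becomes more conservative if the autoregressive form is wrong (about 2–3%). Requiring compound symmetry to agree costs 5–10 points of power: for an assumed 0.6 SD dip at Visit 3 that fully reverses, power falls from 70, 57, 71, 85% to 60, 49, 66, 77% in the four cases.

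### IL-6: Model 1 sets left-censored non-detects to missing on a maximum-likelihood argument that needs data missing at random, and Model 3, which keeps them, is mislabelled

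*Combined protocol and SAP*

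**What the plan says.** All of this is in the Statistical Analysis Plan.

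- **Amount.** "IL-6 had 35% missing data (n=19"). The other markers have between 0 and 3 undetectable values each (0-5.6%). One further IL-6 value was removed under the outlier rule: "Biomarker concentrations greater than three standard deviations from the mean were excluded to limit the impact of statistical outliers on the analysis".
- **Model 1 (primary).** Biomarker "concentrations below the threshold of detectability were treated as missing data in analyses". The reason given is that maximum likelihood in a mixed model copes with missing data without listwise deletion or imputation, "thus making full use of the available data and minimizing bias in parameter estimates".
- **Model 2.** "a secondary model (Model 2) was tested to include a quadratic effect of time for the biomarker outcomes". No different handling of non-detects is described.
- **Model 3.** "a sensitivity analysis model (Model 3) was tested to assess for the effect of data missing at random". In it, values below the threshold "were imputed at half the value of the threshold per the manufacturer".
- **Visits.** The models use Visits 1, 3 and 4. Section 3 (Materials, Methods and Analysis) also has a blood draw at Visit 2. The SAP reports 16 participants starting, 14 completing and 10 returning for Visit 4.

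The SAP states no transformation of the concentrations, no numerical detection limit and no count of non-detects by visit.

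**The concern.** Likelihood-based mixed models protect against bias when the chance that a value is missing depends only on observed data. Here the value is missing because of its own size. Dropping it cuts off the lower tail at every visit, and cuts off more of it at visits where the true level is lower. The mean of what remains is too high, and a real change between visits is distorted.

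The labels run the wrong way round. Model 1 is the model that relies on missing at random, and Model 3 departs from it. A reader would take the better-founded IL-6 analysis for a minor check.

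Aim 1 rests on change in inflammatory markers, and Section 4 says the pilot is meant to produce preliminary data for a full-scale study. A distorted IL-6 change would be carried into that planning.

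**Working it through.** **1. Reproduce the 35%.** 19/54 = 35.2%, 2/54 = 3.7%, 3/54 = 5.6%, and 1/54 = 1.85% (printed as 1.8%). The stated shares therefore fit about 54 samples. On 40 samples (16 + 14 + 10 at Visits 1, 3 and 4) they would be 47.5%, 5.0%, 7.5% and 2.5%, and none match. Since 16 + 14 + 14 + 10 = 54, the denominator appears to include Visit 2, if 14 people attended each of Visits 2 and 3 (an assumption; attendance is not stated).

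**2. Loss inside the modelled visits.** If all 14 Visit 2 values were undetectable, (19 - 14)/40 = 5/40 = 12.5%. If none were, 19/40 = 47.5%. An even spread gives 19 x 40/54, about 14 values (35%).

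**3. Closed form for independent visits, normal scale.** With a proportion p below the threshold, a = Φ⁻¹(p) and λ = φ(a)/(1 - p). The retained mean is too high by λ SD, and a small true change is multiplied by 1 - λ(λ - a). At p = 0.352: a = -0.380, λ = 0.573, and 1 - 0.573 x (0.573 + 0.380) = 0.45. More than half of a small change is lost. Within-person correlation moderates this.

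**4. Large-sample simulation.** Assumed: lognormal values; a fall of 0.5 log-SD at Visits 3 and 4; log-SD 0.5-1.0; correlation 0-0.9; one threshold; attendance in the ratio 16/14/10; AR(1) maximum likelihood with a linear slope; the three-SD rule; no covariates. Estimated slope divided by the complete-data slope:

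| Loss | Model 1, log scale, as written | Non-detects dropped, raw scale* | Half-threshold, log* | Half-threshold, raw* |
|---|---|---|---|---|
| 12.5% | 0.67-0.89 | 0.80-1.08 | 1.01-1.15 | 1.02-1.07 |
| 35% | 0.44-0.75 | 0.62-1.22 | 0.90-1.16 | 1.05-1.13 |
| 47.5% | 0.35-0.68 | 0.55-1.30 | 0.79-1.08 | 1.04-1.12 |

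*Against complete data trimmed by the same three-SD rule, to isolate the non-detect rule. The three-SD rule alone gives 0.98-0.99 on the log scale and 0.68-0.91 on the raw scale.

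At 35% loss the log-scale understatement is 1 - 0.75 = 25% to 1 - 0.44 = 56%. Raw-scale ratios above 1 occur only at correlation 0.9.

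**5. Visit 3 change at trial size** (16/14/10; true changes -0.5 and -0.25 SD at Visits 3 and 4; log-SD 0.7; 35% loss; no outlier rule or covariates). At correlation 0.3, 0.5, 0.7 and 0.9, dropping non-detects gives 0.42, 0.54, 0.64 and 0.84 of the full-data change on the log scale, and 0.77, 0.84, 1.00 and 1.20 on the raw scale. Half-threshold gives 1.00-1.03. A censored-likelihood mixed model on the log scale gives -0.360 and -0.351 at correlation 0.5 and 0.7, against a true -0.35.

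**6. No true change, constant threshold.** The Model 1 slope stays within 0.007 SD of zero. At 35% loss the level is too high by 0.50-0.56 SD (log) or 0.18-0.40 SD (raw).

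**7. Chance of p<0.05 for the linear slope at trial size** (three unrelated time-varying covariates, three-SD rule, log-SD 0.7):

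| Scenario | Dropped | Half-threshold | Complete |
|---|---|---|---|
| Sustained fall, 35% loss, log, correlation 0.3-0.7 | 15-17% | 32-40% | 34-47% |
| Sustained fall, 35% loss, raw, correlation 0.3-0.7 | 10-17% | 24-35% | 26-37% |
| Return to baseline at Visit 4, 35% loss, both scales, correlation 0.3-0.9 | 5-6% | 4-8% | 3-9% |

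A separate run at correlation 0.5 gave 18%, 32% and 35% for the sustained fall at 35% loss. At 12.5% loss, power fell only from 35% (complete) to 23% (dropped). With a return to baseline and 35% loss, every rule gave 7-10%.

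**The case against.** The strongest reply is that the plan already handles the problem: Model 3 puts the non-detects back and has been run. What remains is a rationale, a label and an order of reporting. Promoting a sensitivity model for one of eight markers after the results are known is itself open to dispute, and half-threshold imputation is also ad hoc. Much of this stands, and it limits the severity. It does not rescue the maximum-likelihood argument, which fails whatever the scale or correlation.

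Four stronger readings are tempting, and the documents do not support them:

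- **That Model 1 drops 19 IL-6 values.** The 19 appear to be counted over four visits, and the models use three. Only up to 19 can be said.
- **That a true fall is always understated.** The SAP speaks of concentrations and states no transformation. On the raw scale the bias can vanish or reverse at high correlation.
- **That the chance of detecting a fall is halved.** This needs a fall sustained through Visit 4 and about 35% loss. Section 3 describes Visit 4 as a washout point, 1-10 months after the probiotic, so a return to baseline is at least as natural. A linear slope then has little power under any non-detect rule.
- **That the rule manufactures an effect.** It does not if there is no true change and the threshold and censoring are the same at each visit. If censoring differs by visit, that assurance goes.

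Nor do the documents make IL-6 a lead marker; Aim 1 spans several marker classes.

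**Conclusion.** The point holds for IL-6. Non-detects are left-censored, the stated justification for treating them as missing does not apply, and Model 3 is described as the opposite of what it does. Confidence in that is high.

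Confidence in the size and direction of the bias is moderate, because scale, detection limit, within-person correlation and non-detects by visit are not stated. The IL-6 level is biased upward. A true change is understated on a log scale throughout the range examined. On the raw scale it is understated at low to moderate correlation, with the bias vanishing or reversing at about 0.7-0.9. These figures rest on assumed lognormal values and an assumed fall of 0.5 log-SD. The other seven markers are little affected. Severity is minor to moderate.

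**What to change.** For IL-6 only, and labelled post hoc:

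1. Give as the main IL-6 result an analysis that keeps the non-detects: the existing half-threshold Model 3, with a left-censored (Tobit) mixed model as a check where it converges. Show the treat-as-missing result beside it.
2. Apply the same handling to the quadratic Model 2. Model 3 is not described as having a quadratic term, so it alone would not show a fall that reverses after washout.
3. Remove the claim that maximum likelihood minimises bias for non-detects, and relabel Model 3 as handling left-censored values.
4. Report the analysis scale, the detection limit and the IL-6 non-detects at Visits 1, 3 and 4. These counts would settle most of the remaining uncertainty.

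Leave the other seven markers as they are.

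**Cost.** Mostly wording and reporting order, since Model 3 has been run; the new fits are Model 2 with non-detects kept and the censored check. The downsides are a post hoc label, a different rule for one marker, and single imputation, which can understate uncertainty. In the trial-size sustained-fall runs at 35% loss, however, its 95% coverage was 0.91-0.95, against 0.88-0.96 with complete data. If the modelled loss is near 12.5% there is little or no gain: on the log scale the root mean squared error at correlation 0.3, 0.5 and 0.7 was 0.218, 0.194 and 0.158 with half-threshold, against 0.205, 0.183 and 0.161 with non-detects dropped.

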This pilot project is a brief, open-label clinical trial of probiotics as an intervention to reduce systemic and neural inflammation in heavy drinkers. Heavy drinkers who do not yet show significant signs of liver disease also may stand to benefit from probiotics, but no clinical trials to date have addressed this population. This study will recruit 15 non-treatment-seeking heavy drinkers to complete an open-label within-subjects trial. Aim 1 is to demonstrate proof-of-concept for beneficial effects of probiotic use on inflammatory processes. Aim 2 is to examine effects of probiotic use on brain metabolites correlated with neuroinflammation using magnetic resonance spectroscopy. Aim 3 is to gather preliminary data on acceptability and feasibility of the probiotic intervention in non-treatment-seeking heavy drinkers.

- **Aim 1:** Demonstrate proof-of-concept for beneficial effects of probiotic use on inflammatory processes, as reflected in plasma markers of microbial translocation, immune activation, systemic inflammation, and liver function.
- **Aim 2:** Examine effects of probiotic use on brain metabolites correlated with inflammation using magnetic resonance imaging (MRI).
- **Aim 3:** Gather preliminary data on acceptability and feasibility of the probiotic intervention in the specific population of interest, i.e., non-treatment-seeking heavy drinkers.

If your study ONLY involves the use of identifiable secondary data / biospecimens, including coded data from which you may be able to ascertain participant identity, skip to PART V. Otherwise, please continue to next page.

v. 6/5/2020 Page **5** of **19** 

**3. Materials, Methods and Analysis.** The study design, methods and procedures must be adequately described in order for the IRB to understand all activities in which human subjects will participate. The IRB must also be able to differentiate those procedures that are performed for research purposes from those that are performed for routine care or evaluation.

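### No analysis of Aim 1 is documented as fixed before the data, so Model 1 has no documented confirmatory status and any p-values from it are nominal

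*Combined protocol and SAP*

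**What the plan says.** Protocol Part III section 2 sets Aim 1 prospectively: to "demonstrate proof-of-concept for beneficial effects of probiotic use on inflammatory processes". Section 3 is titled Materials, Methods and Analysis but describes visits and procedures only. Section 4 justifies the sample of 15 completers as suitable for a pilot.

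The Statistical Analysis Plan is in the past tense. Its goal reads "The goal of this analysis was to observe the effect of the probiotic on plasma concentrations of sCD14, sCD163, LBP, IL-6, IL-8, IL-10, MCP-1, and" an eighth marker, TNF-α, with none of the eight ranked above the others. It reports outcomes of the trial: "Of the 16 eligible participants who initiated the probiotic, 14 participants completed the probiotic course, and two were lost to follow-up prior to completion", and "Ten participants returned after the washout period for Visit 4". It counts undetectable and outlying values marker by marker. It then reports modelling decisions as done: "Total number of standard drinks was dropped from the final model due to high VIF"; sex was left out because too few women enrolled; and an autoregressive covariance structure was chosen on AIC. The result is named the primary model (Model 1), followed by a secondary quadratic model (Model 2) and a sensitivity model (Model 3). The section closes with "All analyses in this paper were conducted using SAS software". It carries no date of its own; the protocol is dated October 25, 2022.

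**The concern.** A plan normally fixes the model, outcome, contrast and error rate before results exist. This text cannot have been completed before the results existed, and the protocol does not fill the gap. If Model 1 is read as the planned primary test of an aim to demonstrate an effect, a p-value from it will be given a weight that nothing in the documents supports. That matters most for the full-scale work this pilot is meant to inform: a marker might be carried forward as if it had passed a planned test.

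**Working it through.** **1. What is documented, and where.**

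| Element | Protocol (prospective) | Statistical Analysis Plan (retrospective) |
|---|---|---|
| Aim and marker classes | Aim 1, including liver function | Eight markers, none ranked, none identified as a liver-function marker |
| Blood sampling / visits modelled | Visits 1, 2, 3 and 4 | Visits 1, 3 and 4 |
| Model and contrast | None | Linear mixed model of trajectory; no contrast named |
| Covariates | None | Four drinking variables considered, one dropped on VIF; sex omitted |
| Covariance structure | None | Autoregressive, on AIC |
| Outliers | None | Beyond 3 SD; 1+2+1+1+1 = 6 values removed |
| Undetectable values | None | Missing in Model 1, half the threshold in Model 3 |
| Alpha, multiplicity rule | None | None |

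Only the first two rows have a prospective entry.

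**2. The plan's own figures.** There is no power or alpha to reproduce, so the check is on the undetectable-value percentages. Of the denominators from 30 to 79, only 54 fits all five:
- sCD14: 2/54 = 3.7%
- IL-6: 19/54 = 35.2%
- IL-10: 3/54 = 5.6%
- LBP: 1/54 = 1.85%, printed as 1.8%
- MCP-1: 3/54 = 5.6%

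Visits 1, 3 and 4 supply at most 16 + 14 + 10 = 40 samples, assuming that baseline samples come only from the 16 who started. The other 54 − 40 = 14 then appear to come from Visit 2. Assay results from a visit outside Model 1 were therefore probably in hand when the text was written. There may be a plain reason for leaving Visit 2 out: the plan lists alcohol variables only at Visits 1, 3 and 4. It does not say so, and the narrative in protocol section 3 did intend an alcohol assessment at Visit 2.

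**3. Error from eight co-equal markers.** Assume each is tested two-sided at 0.05, since the documents give no level.
- Independent: 1 − (1 − 0.05)^8 = 0.337.
- Equal pairwise correlation of 0.3, 0.5 and 0.8 (simulated z-tests, 400,000 draws): 0.30, 0.25 and 0.16.
- Bonferroni level for comparison: 0.05/8 = 0.00625.

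**4. Error from the documented selection rules.** A simulation with no true effect used 16, 14 and 10 rows at the three visits and 3,000 runs. The within-person correlation of 0.5 and the covariate correlations were assumed. The critical value of each specification was calibrated so that it alone rejects in 5% of runs. Applying the 3-SD exclusion, the VIF rule and the AIC choice (autoregressive or compound symmetry) gave 5.3% per marker, for both normal and skewed outcomes.
- Monte Carlo standard error: √(0.053 × 0.947 / 3,000) = 0.004, so 5.3% is within one standard error of 5%.
- Over eight independent markers: 1 − (1 − 0.053)^8 = 0.35, against 0.34 for one fixed specification.

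**5. What result-driven choice could do.** Take 2 covariance structures × 3 covariate sets (none, three, four) × outliers kept or removed = 12 versions, and count a marker as positive if any version is significant. One null simulation of about 3,000 runs gave 9.3% per marker, and 1 − (1 − 0.093)^8 = 0.54 over eight independent markers. Other set-ups gave 8.4% (normal outcome) to 11.6% (skewed outcome) per marker: 1 − 0.916^8 = 0.50 to 1 − 0.884^8 = 0.63. These figures measure the room available to an analyst. They do not describe the procedure in the plan.

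**The case against.** The best defence has four parts.

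- **The selection rules are benign.** VIF uses the covariates only, and omitting sex depended on who enrolled. AIC and the 3-SD rule use the outcome, but neither looks at the p-value for time. This stands. A reader might infer from the many post-data choices that the model was picked because it gave a result. Nothing in the documents shows that, and step 4 finds almost no inflation from the stated rules.
- **Primary only ranks the models.** Model 1 is set against a secondary and a sensitivity model, and no sentence says that it was prespecified. This stands in part. The ranking is legitimate, but the word carries a second meaning in a document headed as a plan.
- **The trial is openly modest.** It is an open-label pilot for preliminary data, Aim 1 speaks of proof-of-concept, and the plan's goal is to observe. This stands, and it is why the remedy is mostly wording. The remaining tension is with *demonstrate*.
- **A plan may exist elsewhere.** The documents report results of rules, not when the rules were set, and front pages were removed from the text reviewed. Four named covariates with a VIF cut-off could be a prior rule faithfully applied. This also stands, so the sponsor should not be asked to declare that Model 1 was devised after seeing the data.

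**Conclusion.** The concern holds in a limited form. Aim 1 was stated prospectively; what is missing is any analysis documented as fixed before the data. Model 1 therefore has no documented confirmatory status, and any p-values are nominal. It would go too far to call Aim 1 itself post hoc, or to say that the analysis was chosen for its results.

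The main error comes from eight uncorrected, co-equal markers: about 34% if independent, and about 16% to 30% at pairwise correlations of 0.8 down to 0.3. The documented selection adds roughly one to two percentage points to the independent figure, which is within simulation error. The 9.3% per marker and 54% over eight markers are upper bounds for that simulation set-up, and they would require choosing among versions by p-value.

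All of this rests on an assumed two-sided 0.05 and on the stated simulation assumptions. Because each version was calibrated to 5%, the simulations do not address whether the mixed-model tests are themselves accurate with 16 participants.

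**What to change.** 1. Supply a dated earlier analysis plan if one exists, and mark where Model 1 follows it.
2. Otherwise, in the linear mixed model paragraph of the Statistical Analysis Plan, label Model 1 exploratory and state that no analysis was documented before the data. The ranking of Models 1 to 3 can stay.
3. For all eight markers, report the Visit 3 minus Visit 1 change as an estimate with a 95% confidence interval. This is the direct on-treatment contrast, whereas a single slope over Visits 1, 3 and 4 runs through the washout visit.
4. Add a short sensitivity table per marker: outliers kept versus removed; drinking covariates none, three or four; and the covariance structures that were compared.
5. Word the Aim 1 conclusion as exploratory, and do not describe an effect as demonstrated.

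No new data are needed. The cost is some rewording, a modest set of reruns of existing models, and a less favourable claim.
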